The primary study outcome is pain response at 12 months, defined as a 30% improvement in the Brief Pain Inventory (BPI). The main opioid dose outcome is 50% reduction in opioid daily dose. The main composite outcome is the proportion with 30% improvement in pain and 50% decrease in opioid daily dose, representing dual improvements in pain and opioid safety. We will assess secondary patient-relevant outcomes including function, quality of life, symptoms (e.g., depression, anxiety, sleep, fatigue), and adverse effects.

Analytic methods

All participants will be assessed in the arms to which they are assigned. An estimated sample size of 970 patients from 10 sites provides 80% power for a 2-sided chi-squared test comparing pain response rates for TCM and IPT if IPT adds 10% to the response rate, and $> 85\%$ power if IPT adds 11% to the response rate. We will use all follow-up data in repeated-measures logistic regression modeling 30% reduction from baseline in BPI scores. For the second aim, we estimate 80% power power to detect small to moderate effects (Cohen d or standardized difference) in mean BPI scores of 0.35 or more.

We will evaluate heterogeneity of treatment effects in 5 pre-specified subgroups that may be differentially responsive to treatment, at greater risk for opioid harms, or more likely to have difficulty reducing opioids (patients treated with high-dose opioids and those with depression symptoms, post-traumatic stress symptoms, potential substance use disorder (SUD), and fibromyalgia symptoms). We will use repeated-measures linear regression to examine interactions of subgroup with treatment assignment.

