1.2 Secondary Objectives

1.2.1 Subgroup analyses

We will examine differential response to TCM and IPT among subgroups of study participants. Subgroups are not mutually exclusive and are defined as presence (yes/no) of the following characteristics at baseline:

- High-dose opioid therapy (≥ 70 ME mg/day)
- Depression symptoms
- Post-traumatic stress symptoms
- Potential SUD
- Fibromyalgia symptoms

We hypothesize that IPT will be superior to TCM in the following subgroups: high-dose opioid therapy, depression, post-traumatic stress, and SUD.

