7.1.2 Subgroup power estimates

A difference of 1 unit in BPI is considered clinically significant and the SD of the BPI scores is typically about 2 units. A sample size of 776 participants at the 12-month

assessment will provide $> 80\%$ power for detecting a clinically meaningful difference in intervention effects across subgroups with prevalence of at least 40%, assuming a Bonferroni corrected significance level of 0.01. For a 1.2-unit difference in intervention effects, the study will have $> 85\%$ power for subgroup prevalence of 25% or more. Within a subgroup, the study will have $> 80\%$ power to detect an intervention effect of 1 unit or more for subgroup prevalence of $> 25\%$ and a 0.01 significance level. These power calculations for comparisons of 12-month outcomes consider just the data for this assessment point as a worst-case scenario. The repeated measures analyses discussed below should have power greater than discussed here for comparing the 12-month outcomes. Based on preliminary data, we anticipate the proposed sample size will provide adequate power for planned assessments of the HTE for all planned subgroups; if prevalence of any subgroup is $< 25\%$, assessment of HTE across subgroups will be exploratory.

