7.4 Pre-Specified Subgroup Analyses

We will examine variation in the intervention effects on the change in BPI within clinical subgroups defined by presence or absence at baseline of the subgroup status/conditions described above. For each subgroup measure, we will fit a repeated-measures linear regression modelling change from baseline in BPI at the quarterly follow-up assessments using assigned intervention, assessment point, subgroup indicator and all interactions between these three measures together with baseline BPI score and its interaction with assessment point as explanatory measures. Assessment points will be incorporated as random effects, with an unstructured covariance, to model potential correlation among outcomes for individuals. Our primary assessment of an interaction between intervention and the subgroup measure will use the model-based two-sided Wald test for an interaction at the 12-month assessment, using a 0.005 significance level. Weighted selection model analyses similar to those described above will examine sensitivity of 12-month results to response biases.

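### Section 1.2.1 hypothesises that IPT is superior within four subgroups and 7.1.2 powers a within-subgroup effect at 0.01, but the only test 7.4 names is the interaction at 0.005

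*Combined protocol and SAP*

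**What the plan says.** Section 1.2.1 sets the objective: "We will examine differential response to TCM and IPT among subgroups of study participants". It lists five subgroups and then states a directional hypothesis for four of them, leaving out fibromyalgia: "We hypothesize that IPT will be superior to TCM in the following subgroups", the four being high-dose therapy, depression, post-traumatic stress and SUD.

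The analytic methods in the abstract speak only of interactions: "We will use repeated-measures linear regression to examine interactions of subgroup with treatment assignment".

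Section 7.1.2 gives three power statements, all at a Bonferroni level of 0.01 with 776 patients:

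- more than 80% for a 1-unit difference in effects between subgroups, at 40% prevalence or more;
- more than 85% for a 1.2-unit difference, at 25% or more;
- for an effect inside one subgroup, more than 80% "power to detect an intervention effect of 1 unit or more for subgroup prevalence of" above 25%.

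Section 7.4 fits treatment, assessment point and subgroup with all their interactions. Its primary assessment of the interaction "will use the model-based two-sided Wald test for an interaction at the 12-month assessment", "using a 0.005 significance level". It names no within-subgroup contrast, no alpha for one, and no rule for reading one beside the interaction.

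**The concern.** Superiority in a subgroup and a larger effect in that subgroup than outside it are different claims. The first concerns the IPT-TCM difference in one stratum. The second concerns the gap between two strata. The interaction test addresses only the second.

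The two can part company in a plausible case. Section 7.1.1 powers Aim 1 for an IPT gain across the whole sample. If that gain is broad, IPT may be superior in every named subgroup while the interaction is close to zero.

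At stake is what may be claimed about which patients benefit. Because the plan does not say which result bears on the hypothesis, someone holding the data could choose between an interaction and a stratum contrast, and between 0.01 and 0.005. In addition, one of the stated powers belongs to a comparison that the analysis section does not specify.

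**Working it through.** **Inputs from the protocol.** N = 776 at 12 months, which is 80% of 970 (7.1). BPI SD about 2, effect 1 unit, alpha 0.01 (7.1.2). Alpha 0.005 (7.4). Equal allocation to TCM and IPT (4.3.9). High-dose share 35% (7.1.1). Prevalences of 25% and 40% are the thresholds in 7.1.2.

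**Assumption.** The IPT effect outside the subgroup is not given, so a range is shown.

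**Formulas** (normal approximation, two-sided, 12-month data only, p = subgroup prevalence):

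- Within a subgroup, N·p/2 patients per arm: SE = 2·√(2/(N·p/2)) = 4/√(N·p).
- Interaction: SE = 4/√(N·p·(1−p)).
- Power = Φ(effect/SE − z), with z = 2.576 at 0.01 and 2.807 at 0.005. The interaction figures also count the opposite tail.

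**Step 1: reproduce 7.1.2, then move to the alpha in 7.4.**

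| Statement in 7.1.2 | SE | Stated | At 0.01 | At 0.005 |
|---|---|---|---|---|
| Interaction, 1 unit, p = 0.40 | 4/√186.24 = 0.293 | >80% | 79.8% | 72.7% |
| Interaction, 1.2 units, p = 0.25 | 4/√145.5 = 0.332 | >85% | 85.1% | 79.2% |
| Within subgroup, 1 unit, p = 0.25 | 4/√194 = 0.287 | >80% | 81.8% | 75.0% |

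All three reproduce at 0.01; the first falls short of its threshold by 0.2 points, which I treat as rounding. None reaches its stated threshold at 0.005.

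**Step 2: the same truth under the two tests.** IPT is better by 1 unit inside the subgroup, so the 1.2.1 hypothesis is true in every row.

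| Effect outside the subgroup | p = 0.25 | p = 0.35 | p = 0.40 |
|---|---|---|---|
| Within-subgroup contrast at 0.01 (any effect outside) | 81.8% | 93.9% | 96.6% |
| Interaction at 0.005: 1 unit outside | 0.5% | 0.5% | 0.5% |
| Interaction at 0.005: 0.75 unit outside | 2.0% | 2.4% | 2.6% |
| Interaction at 0.005: 0.5 unit outside | 9.7% | 12.6% | 13.5% |
| Interaction at 0.005: 0.25 unit outside | 29.3% | 37.6% | 40.2% |
| Interaction at 0.005: 0 outside | 58.3% | 69.7% | 72.7% |

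The difference in alpha explains little of the gap. With the contrast also at 0.005, its power is 75.0%, 90.5% and 94.5%. With the interaction at 0.01 and 0.5 unit outside, its power is 14.3%, 18.0% and 19.2%.

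Repeated measures and baseline adjustment should raise the power figures. They cannot raise the 0.5% under a uniform effect, which is simply the test's alpha.

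**The case against.** The strongest reply is that the subgroup aim is heterogeneity. Section 1.2.1 opens with differential response, and the abstract and Section 4.3.2 both speak of heterogeneity of treatment effect. Naming four of five subgroups makes more sense as a differential claim than as a uniform benefit. On that reading 7.4 tests what was meant, and 1.2.1 is only loosely worded. This stands in part: the interaction is the right test for that aim and should stay. It does not make the printed hypothesis a statement about interaction, and it leaves the within-subgroup power in 7.1.2 without a specified analysis.

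A reader might infer that the four hypotheses go untested, or that the trial will accept or reject them on the interaction p-value. The documents support neither. Section 7.1.2 foresees the within-subgroup comparison, the 7.4 model yields it directly, and the sentence on the Wald test says how the interaction is assessed, not that nothing else will be estimated. No section says that the interaction decides the 1.2.1 hypotheses.

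It is also fair to say that a uniform 1-unit benefit would not be missed overall. The whole-sample SE of the mean difference is 4/√776 = 0.144, so z is about 7 and power exceeds 99.9%. Reporting no heterogeneity would then be correct. What would be missing is an agreed way to state the result for the four subgroups.

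The reverse case can be constructed. With no IPT effect inside a 40% subgroup and TCM better by 1 unit outside it, the interaction is significant 72.7% of the time although IPT is not superior in the subgroup. Nothing in the plan anticipates this pattern, so the point does not rest on it.

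**Conclusion.** The concern holds as a mismatch among three sections: a within-subgroup hypothesis in 1.2.1, power for both kinds of effect at 0.01 in 7.1.2, and a single named test, the interaction at 0.005, in 7.4. The within-subgroup comparison is foreseen and can be estimated, but it is not specified as an analysis.

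The size depends on the effect outside the subgroup, which is assumed. At the prevalences examined, the interaction test's chance of rejecting when the hypothesis is true runs from 0.5% under a uniform benefit to 58% to 73% when there is no benefit outside. The 0.01 versus 0.005 conflict is separate and needs no such assumption: the powers in 7.1.2 do not apply to the test in 7.4. The value 0.005 equals 0.05/10, which would fit five subgroups with two tests each, but the documents do not explain it.

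Severity is minor to moderate. This is a secondary objective and the primary analysis is unaffected.

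**What to change.** 1. Keep the interaction as the test of heterogeneity and reword the hypothesis in 1.2.1 to match: IPT's advantage over TCM will be larger in the four named subgroups than outside them.
2. In 7.4, pre-specify the 12-month IPT-TCM difference with its confidence interval in each stratum, estimated from the same model.
3. Limit any claim of superiority within a subgroup to the four hypothesised subgroups. Rest it on that contrast, with the interaction result reported beside it. All other stratum estimates are descriptive. Without this limit, ten stratum contrasts at 0.01 plus five interactions at 0.005 would sum to 10 × 0.01 + 5 × 0.005 = 0.125.
4. State one alpha for the interaction family and one for the contrast family, and use each in both 7.1.2 and 7.4. As arithmetic guides, five interactions at 0.01 sum to 0.05, and four contrasts at 0.01 sum to 0.04. If 0.005 is kept for both, restate the three powers as about 73%, 79% and 75%. Set the confidence level of each stratum interval to match the chosen alpha.

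The cost is wording plus contrasts from a model already planned. No new data are needed. The changes should be dated before arm-level outcome data are examined.

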1.2.2 Secondary outcomes

We will examine intervention effects on the following additional patient-reported outcomes:

- Pain intensity
- Pain interference with function
- Quality of life
- Adverse symptoms
- Fatigue
- Sleep
- Mental health
- Substance use
- Use of nonpharmacological therapies

We will examine intervention effects on the following additional opioid dose outcomes:

- Proportion with 25% dose reduction from baseline to 12 months
- Proportion with any dose reduction from baseline to 12 months
- Mean dose change from baseline to 12 months
- Proportion with dose escalation (increase in opioid daily dose of $\geq 25\%$ from baseline to 12 months)

1.2.3 Predictors of variation

We will examine variation in intervention effects by sex, study site and time over the course of enrollment, as well as moderation of effects by relevant covariates.

1.2.4 Implementation Process Evaluation

Aim 3 is to understand patients' and clinicians' experiences with the study interventions and identify strategies to enhance future implementation and dissemination of effective pain care interventions.

Data will be gathered to examine patients' and clinicians' perceptions of the interventions; to describe the context and processes of intervention delivery; and to assess potential for long-term sustainability and widespread dissemination of the interventions. Data collection methods will include in-depth semi-structured interviews with patient and clinician participants and other VA employees; unstructured conversational interviews with researchers, clinicians, and stakeholders; and observation of research and intervention implementation processes.

Goals of this approach are threefold: 1) to increase the relevance of the primary research findings to patients, clinicians, and health care decision-makers; 2) to increase the likelihood of timely translation of research findings into diverse practice settings; and 3) to generate information to guide interpretation of primary trial findings. In addition to scientific reports and manuscripts, products of this process evaluation will include an

implementation toolkit (developed in collaboration with study partners) to support implementation of successful study interventions in diverse practice settings.

2. BACKGROUND AND RATIONALE

2.1 Chronic Pain and Opioid Therapy

Chronic pain affects approximately 100 million Americans, with an estimated \$560-635 billion in annual health care and lost productivity costs. Furthermore, three of the top five causes of years lived with disability are painful conditions—back pain, neck pain, and other musculoskeletal disorders. Starting in the early 1990s, improved awareness of the burden of pain and concern about pain under-treatment drove a generalized expansion in opioid analgesic prescribing. Tragically, this expansive prescribing has triggered a new epidemic of opioid-related deaths and addictive disorders, while meaningful progress toward the original goal—reducing the burden of pain—has not been demonstrated.

For many patients receiving long-term opioids for chronic pain, potential harms of continuing opioid therapy outweigh benefits. Indeed, benefits of long-term opioid therapy are often elusive. Most patients receiving long-term opioid therapy continue to experience severe pain and functional limitations. Counter to prior assumptions, studies have found that higher opioid doses are not associated with corresponding improvements in analgesic response. Patients prescribed higher-dose opioids may have worse quality of life than those receiving low-dose or no opioids.

The frequency and severity of opioid-related harms among patients receiving long-term opioid therapy for pain are increasingly evident. Harms stemming from pharmacological properties include tolerance and physical dependence in most persons with long-term exposure and addiction in a substantial minority. Further, opioid involvement in respiratory control mechanisms can cause unpredictable fatal respiratory suppression when dosages are miscalculated or increased rapidly, too many pills are taken, or other drugs or conditions interact to potentiate opioid effects or cause buildup of toxic levels. Prescribed opioid dosage seems to be a major driver of risk for these and other harms.

For patients with chronic pain on long-term opioid therapy, pain management should involve attention to both improving pain and reducing risk for opioid-related harms. Evidence supports the effectiveness of a wide variety of non-opioid therapies for improving chronic pain outcomes, but response to treatments is variable and individual therapies typically generate only partial improvement. Thus, multi-modal integrated care is favored as the optimal pain management approach.

Unfortunately, little evidence is available for strategies to reduce or discontinue opioid therapy while managing pain. Although comprehensive pain rehabilitation programs have demonstrated success, expansion of these programs to accommodate vast numbers of patients on long-term opioid therapy is not likely. As most patients on opioid therapy for chronic pain are treated in primary care settings, evidence is needed for strategies to support deliver improved pain and opioid management in primary care.

2.2. Study Rationale

Our work has identified numerous barriers to improving pain and opioid management in primary care, including ineffective communication, patient and provider knowledge deficits, limited time and appointment availability, and insufficient resources in terms of clinical staff,

assessment tools, and treatment pathways. The 2014 NIH Pathways to Prevention opioids for chronic pain panel concluded that individual clinicians “are often overburdened and have insufficient resources,” so “systems of care must facilitate implementation” of pain and opioid management guidelines.

In VA, national pain management and opioid safety initiatives direct local facilities to increase use of nonpharmacological pain care and improve opioid management, but clinical leaders at each facility must decide how to achieve these objectives. As in non-VA health care settings, clinical leaders need direct and high-quality evidence to guide decisions about how to allocate finite resources to achieve dual goals of improving pain while reducing opioid use. This study compares two systems of care strategies that each use patient-centered approaches to address barriers to improved pain and opioid management in primary care.

Our overall approach is informed by our engagement with patient partners, who strongly emphasize the primary need for individualized pain care and longitudinal support to achieve pain management goals. A second point of partner emphasis was the need to address potential mistrust toward a health care system that initiated many Veterans on long-term opioids and now could be seen as pulling “the rug out from under [them].” Accordingly, the central focus of our interventions is on optimizing pain care. Likewise, our primary outcome is improvement in pain.

2.2.1 Rationale for TCM intervention

TCM is the low-intensity pain management intervention. It is based on the three component model, initially developed as a structured approach to addressing primary care barriers to depression care and subsequently extended to pain care. In the TCM arm, the central care provider is a pharmacist care manager who has regular follow-up visits with the patient and delivers care in collaboration with a consulting physician and the primary care team.

TCM effectiveness for chronic pain has been demonstrated in multiple trials. In the SCOPE trial of TCM vs. usual care for chronic pain, participants in the TCM arm were nearly twice as likely to have a clinically important improvement in pain at 12 months. A pre-specified subgroup analysis found a positive response to the intervention among the third of study participants who were on opioids at baseline. TCM has not been specifically tested as an approach to achieve opioid dose reduction, but it was easily extended to include opioid tapering in the VA-funded SPACE trial.

In patient-facing and public-facing materials (e.g., study brochure, recruitment letter), TCM will be referred to as “pharmacist pain care.”

2.2.2 Rationale for IPT intervention

IPT is the higher-intensity pain management intervention. It is based on the biopsychosocial model, which is the dominant heuristic to explain chronic pain as a complex phenomenon determined by biological inputs, as well as factors such as mood, cognitions, relationships, and health care systems issues. In the IPT arm, an interdisciplinary team delivers biopsychosocial care emphasizing multimodal pain management and behavioral activation.

IPT effectiveness is supported by indirect evidence from trials of other interdisciplinary pain programs and observational evidence from similar programs implemented in VA.

RCTs have demonstrated the effectiveness of a variety of interdisciplinary pain programs that combine medical, psychological, and exercise approaches, as in the IPT arm. Further, several observational reports suggest that IPT clinics can improve care. For example, the Integrated Pain Clinic at the West Haven VA—staffed by a physician, psychologist and physical therapist—demonstrated improvement in patient and provider pain treatment satisfaction.

In patient-facing and public-facing materials (e.g., study brochure, recruitment letter), IPT will be referred to as “integrated pain care.”

2.2.3 Rationale for expanded taper options intervention

All patients in the study will receive standard information about opioid tapering, which typically involves gradually decreasing daily doses of opioids over time. Patients randomized to the expanded options arm will receive information about buprenorphine rotation as an optional component of their personal treatment plan. Patients who opt in to buprenorphine rotation will complete a separate informed consent process for the buprenorphine rotation research protocol.

Rotation to buprenorphine, a partial opioid agonist with analgesic properties similar to those of other opioids, may help patients reduce opioid use by effectively treating the opioid withdrawal syndrome while allowing more rapid dose reduction. Opioids cause physical dependence in most persons with long-term exposure. In physical dependence, interrupting or stopping opioids causes unpleasant withdrawal symptoms, which include increased pain and dysphoria and sometimes opioid craving. These problems are major barriers to opioid discontinuation, both for persons who use opioids illicitly and for those who take prescribed opioids. Slowly reducing opioid doses over time (usually over months) can prevent development of withdrawal symptoms, but some patients on high opioid doses may prefer a more rapid approach facilitated by buprenorphine rotation.

In patients with opioid use disorders, strong evidence from multiple RCTs supports buprenorphine effectiveness for achieving sustained abstinence from illicit opioids. Observational evidence suggests buprenorphine is similarly effective for successful discontinuation of full-agonist opioids in patients on long-term opioids for pain and that patients transitioned from high-dose opioids to buprenorphine often have improved pain/function and decreased opioid AE.

